## **3. STUDY DESIGN**

This is a multi-center, observational study involving retrospective collection of NSCLC patients information. All consecutive patients who had a newly diagnosis of NSCLC in 2017 from healthcare administrative database and received at least one anti-cancer drug treatment between January 2017 and December 2017, identified through the proposed algorithm, will be considered. All data needed for KPI calculation, even if they fall outside January-December 2017 period, will be collected. The end of data collection will be defined as patient death or 30 June 2018, whichever came first.

A set of potential KPIs had been developed from a panel of experts (clinicians, IT experts etc..) to investigate the appropriateness of activities within NSCLC care pathway, with a special focus on the use of immunotherapy.

The eligible population and data will be gathered retrospectively through an algorithm from administrative databases (SDO, REM, ASA, FED, AFT, ADI, SDHS-hospice).

Administrative data will be used as unique resource:

- to identify patients cohort;
- to measure KPIs along care pathway ;

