##### **4.1 Definition of study groups**

An algorithm will be developed to reliably identify eligible subjects from administrative database SDO. The algorithm will apply specific criteria to patients collected in administrative databases from January 2017 to December 2017. It will be developed as the combination of ICD-9-CM codes with other criteria. Selection of codes and criteria was based on a discussion between senior Oncologists with expertise in lung cancer and the outcome research working group at IRST.

A first data extraction from the administrative database will be performed to identified potential study subjects. These data are related to patients with at least one hospitalization due to diagnosis of malignant tumors of trachea, bronchi and lungs between January and December 2017 using the International Classification of Diseases, 9th EDITION, (ICD-9-CM codes: 162\* in all position of diagnosis codes).

The following criteria will be applied to obtained patients, to exclude prevalence NSCLC cases (incident cases in 2014-2016 period), patients with mesothelioma (cod 163\*) and SCLC patients in order to obtain the correct population.

- Only NSCLC incident cases in 2017 will be considered, excluding prevalence cases that had the same diagnosis in the 3 years before the period of interest (2014-2016). Patients with at least one hospitalization due to diagnosis of malignant tumors of trachea, bronchi and lung according to ICD-9CM 162\* in the 3 years prior to the first index hospitalization on the year of evaluation (2017) will be excluded

- Patients with at least one hospitalization due to malignant tumor different than tumors of trachea, bronchi and lungs (ICD-9CM 140\*-161\* or 163\*- 195\* or 200\* - 208\* or V.10\* excluding V10.11 and V10.12), in the 3 years previous 2017 should be excluded.
- All patients with at least one ATC Code L01CB01
- Etoposide (VP-16) therapy administration in the 180 days following the first hospitalization index will be excluded.

After criteria application, the final population shall include only NSCLC patients.

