## **5 STUDY PROCEDURES AND DATA COLLECTION**

To evaluate primary objective of the study, patient information will be obtained only from regional administrative databases both for out-patient and in-patient settings. These data will be related only to the year 2017.

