11	
KPIs on THERAPIES For patients enrolled in experimental clinical trial will not be possible to retrieve information on therapies from administrative database.
 
a) Percentage of patients treated with immunotherapies NUM: Patients with at least one administration of immunotherapy According to Anatomical Therapeutic Chemical Classification System ATC, the following codes will be investigated: L01XC17 nivolumab L01XC18 pembrolizumab L01XC32 atezolizumab
 
DEN: Total number of patients identified by the algorithm who underwent anti-cancer drug treatment for NSCLC, as single or double agent chemotherapy, target therapy etc..(excluded neoadjuvant patients of KPI 5)
 
b) Percentage of patients who underwent immunotherapy for more than 6 months after first dose. NUM: Number of patients who underwent immunotherapy more than 6 months after the first administration; DEN: Total number of patients identified by the algorithm who underwent immunotherapy;

12	
Percentage of patients who underwent anti-cancer drug treatment in the last 30 days of life NUM: Number of patients who underwent anti-cancer drug treatment in the last 30 days of life; DEN: Total number of patients identified by the algorithm who deceased

13	
Percentage of patients who underwent the first administration of systematic anti-cancer drug within 30 days from discussed in MDT meeting NUM: Number of patients who underwent first systematic anti-cancer drug administration within 30 days from MDT; DEN: Total number of patients patients identified by the algorithm discussed in MDT meeting;

14	
Percentage of patients who underwent RT in the last 30 days of life ( excluded palliative treatments single fraction) NUM: Number of patients who performed RT in the last 30 days of life ( excluded palliative treatments); DEN: Total number of patients identified by the algorithm who deceased;

15	
Percentage of patients who underwent at least one Integrated Home Care (IHC) NUM: Number of patients who underwent IHC service; DEN: Total number of patients identified by the algorithm;

16	
Percentage of patients who underwent at least one hospice care NUM: Number of patients who underwent hospice care; DEN: Total number of patients identified by the algorithm;

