### **7.3 Data analysis**

For primary objective, for each indicator, the proportion of patients who receive the procedure, in the defined time window, among those eligible will be calculated. Descriptive statistics as arithmetic mean and standard deviation (SD) as well as median value and minimum–maximum statistics will be presented for KPI related to average time. Two-sided 95% confidence interval (95% CI) will be reported as appropriate and specified for KPI expressed as proportion. For secondary objective, the validity of algorithm will be evaluated by individual matching among cases retrieved from administrative database and medical chart obtained from IRST. Following definition will be used to explain this objective: NSCLC cases appearing as incident cases in administrative database, but not in IRST clinical chart will be considered as false positive and those appearing in IRST clinical chart but not in administrative database will be considered as false negatives.

Sensitivity will be defined as the percentage of NSCLC cases correctly identified by the algorithm and calculated as the proportion among NSCLC cases identified both in administrative database and IRST clinical chart ('true positive' cases) and all cases identified as NSCLC cases from IRST clinical chart ('true positive' + 'false negative' cases). Positive predictive value will be defined as the percentage of NSCLC patients identified from IRST clinical chart were really NSCLC. This proportion will be calculated as the proportion among NSCLC cases identified both in administrative database and IRST clinical chart ('true positive' cases) and all cases identified as NSCLC cases from administrative database ('true positive' + 'false positive' cases).

Likewise, specificity and negative predictive value will be calculated, and exact (Clopper-Pearson) 95% confidence limits for binomial distribution will be applied.

Statistical analysis will be performed using Stata software 15.1/SE for Windows (Stata Corp LP, USA).

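### KPIs 15 and 16 count any home-care or hospice use without a window or anchor date, while potential follow-up runs from 181 to 545 days

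*Protocol*

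**What the plan says.** Protocol Section 5.2 defines KPI 15 as "NUM: Number of patients who underwent IHC service; DEN: Total number of patients identified by the algorithm". KPI 16 is titled "Percentage of patients who underwent at least one hospice care" and defined as "NUM: Number of patients who underwent hospice care; DEN: Total number of patients identified by the algorithm". Neither row gives a start date or a time limit.

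Section 7.3 says that for each indicator "the proportion of patients who receive the procedure, in the defined time window, among those eligible will be calculated".

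Three other sections determine how long a patient is observed:

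- Section 4.1 takes patients with "at least one hospitalization due to diagnosis of malignant tumors of trachea, bronchi and lungs between January and December 2017".
- Section 3 adds that "All data needed for KPI calculation, even if they fall outside January-December 2017 period, will be collected", and that "The end of data collection will be defined as patient death or 30 June 2018, whichever came first".
- Section 5, on data for the primary objective, says "These data will be related only to the year 2017".

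Most neighbouring indicators do carry a limit: 7 days (KPIs 1 and 8), 6 months (KPI 5), 30 days (KPIs 6, 12, 13 and 14) and the year of incidence (KPI 7). KPIs 12 and 14 also use deceased patients as the denominator.

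**The concern.** A proportion who have ever used a service rises with the time over which use can be seen. Here that time is set by a common calendar cut-off, so it depends on when in 2017 the patient was admitted. Someone alive on 30 June 2018 who has not yet used the service counts as a non-user, whether they were observed for six months or for eighteen.

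Home care and hospice tend to come late in the pathway, so these two indicators are more exposed to this than most. Section 2.1 wants the KPIs to describe appropriateness and quality of care among the sites. A percentage with no stated time meaning serves that poorly: part of any difference could reflect the mix of index dates, or the cut-off chosen, rather than the care given.

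**Working it through.** The protocol states no usage rate and no follow-up length, so there is no figure of its own to reproduce. The dates come from the protocol; the rates are assumptions.

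**1. Potential follow-up (Sections 4.1 and 3).** Days from index admission to 30 June 2018:

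- index 1 January 2017: 545 days
- index 1 July 2017: 364 days
- index 31 December 2017: 181 days

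The longest is 545/181 = 3.0 times the shortest. If Section 5 governed and data stopped on 31 December 2017, the range would be 364 days down to 0.

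**2. Effect of follow-up under a constant rate of first use.** Death is ignored, and q is the assumed 12-month use. Then h = −ln(1 − q)/12 per month, and use by month t is F(t) = 1 − exp(−h·t) = 1 − (1 − q)^(t/12).

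- q = 25%: F(6) = 1 − 0.75^0.5 = 13.4%; F(18) = 1 − 0.75^1.5 = 35.0%.
- q = 40%: F(6) = 1 − 0.60^0.5 = 22.5%; F(18) = 1 − 0.60^1.5 = 53.5%.

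**3. The figure the study would actually report.** This is one proportion over a full year of index dates. With dates uniform over 2017, follow-up is uniform on (a, b) months and the expected proportion is 1 − [exp(−h·a) − exp(−h·b)] / [h·(b − a)].

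| Assumed 12-month use | Section 3 cut-off (a = 6, b = 18) | Section 5, 2017 only (a = 0, b = 12) |
|---|---|---|
| 25% (h = 0.02397) | 24.7% | 13.1% |
| 40% (h = 0.04257) | 39.3% | 21.7% |

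Under Section 3 the pooled figure sits close to 12-month use. Which section is followed makes a larger difference to the reported value: nearly two-fold for identical care.

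**4. Hospice use tied to death.** Assume exponential survival with median m months and a share c of decedents using hospice, so that recorded use by month t is c·(1 − 2^(−t/m)).

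- m = 12, c = 40%: 0.40 × 0.293 = 11.7% at 6 months and 0.40 × 0.646 = 25.9% at 18 months.
- Over m = 8 to 18 and c = 20% to 60%: from 4.1% against 10.0% (m = 18, c = 20%) to 24.3% against 47.4% (m = 8, c = 60%).
- The ratio of 18-month to 6-month use is 1.9 to 2.4, depending only on m.

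**5. Size of a site effect.** Moving a site's mean index date by one month (follow-up uniform on 5 to 17 months instead of 6 to 18) changes the pooled KPI by about 1.8 points at q = 25% and 2.6 points at q = 40%. If the roughly 400 patients split equally (assumption, about 133 per site), the 95% half-width is 1.96 × √(0.25 × 0.75/133) = 7.4 points, or 8.3 points at 40%.

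**The case against.** Several objections have force.

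- **There is an implicit window.** Section 3 closes observation for everyone at death or 30 June 2018, so the rows can be read as use from index to that date. That is fair, but such a window differs threefold in length between patients, and Section 5 contradicts its end date.
- **The contrast between 1 January and 31 December patients is never reported.** This stands. With uniform index dates the pooled proportion is near 12-month use. A reader might infer that the percentage has no meaning at all; step 3 does not support that.
- **Sites share the same index year and cut-off.** This also stands. A reader might infer that the sites cannot be compared. The protocol gives no reason to expect different index-date mixes, and step 5 shows that a one-month shift is small beside sampling error. Bias needs a difference in index-date mix, or in survival that changes how many patients are cut off. Patients who die before the cut-off are fully observed. Comparison with later years is not planned in the protocol.
- **The rates are assumed.** Correct. A spread of more than two-fold is not universal: the ratio is 1.9 when median survival is 8 months.
- **The KPI list is provisional and an analysis plan could supply windows.** The table is marked as a draft and the KPIs are called potential. But the protocol itself fixes numerator and denominator and relies on a window that these two rows do not give.
- **A 180-day window alone is a poor replacement.** This stands. At q = 25% it keeps 13.4/25 = 54% of 12-month users, so it should not be the only headline figure.

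**Conclusion.** The point holds as a minor one. KPIs 15 and 16 lack the window that Section 7.3 presupposes, and under Section 3 potential follow-up ranges from 181 to 545 days. The crude percentage therefore depends on the index-date mix and the cut-off. Recorded use for the latest against the earliest index dates would be 13.4% against 35.0% if 12-month use is 25%, and 22.5% against 53.5% if it is 40%. Both pairs rest on an assumed constant rate with death ignored; linking hospice use to death gives 11.7% against 25.9% in the central case.

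The documents do not support saying that the pooled figure is meaningless or that site comparisons are invalid. The first is close to 12-month use if index dates are even, and the second are biased only under the differences described above. The sharper problem for the reported value is the conflict between Sections 3 and 5, which under the same assumptions moves the pooled KPI from 24.7% to 13.1%, or from 39.3% to 21.7%.

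**What to change.** First reconcile Section 5 with Section 3 on the period the data cover. The rest assumes the Section 3 cut-off; under a 2017-only rule, only patients indexed by 4 July 2017 could be observed for 180 days.

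Then, in Section 5.2:

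1. Anchor both KPIs at the index admission.
2. Report use within 180 days, which every patient reaches (or dies before) by 30 June 2018, since the shortest potential follow-up is 181 days.
3. Beside it, report the cumulative incidence of first use to 12 months, with death as a competing event and censoring at 30 June 2018.
4. For hospice, also report the proportion among deceased patients, as KPIs 12 and 14 do. This reduces the problem rather than removing it, because who has died by the cut-off still depends on follow-up.
5. Keep the any-time proportion as a supplement, labelled with its range of follow-up.

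The cost is a clause per KPI, a date filter and one additional estimator, with no data beyond what Section 3 already collects. The downside is a little more analysis, and the 180-day figure leaves out later use, which is why it is paired with the 12-month estimate.

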### 5.2 Key performance indicators for monitoring care pathway in NSCLC patients

The following key performance indicators (KPIs) will be measured to investigate the appropriateness of NSCLC patient care pathways, with a special focus on the use of immunotherapy.

[figure not shown]
BOZZA - KPI -	
1	
Percentage of patients who performed biopsy within 7 days from the date of examination prescription
 
NUM: Number of patients who performed biopsy within 7 days from prescription; DEN: Total number of patients identified by the algorithm who performed biopsy;

2	
Percentage of mNSCLC patients at diagnosis
 
NUM: Number of patients with metastases (presence of one of the following codes (197*,198*,199*) in all position of diagnosis codes for index hospitalization); DEN: Total number of patients identified by the algorithm;

3	
Percentage of major surgical resections within the year of analysis.
 
NUM: Number of patients who underwent to lung cancer major surgical resection; DEN: Total number of patients identified by the algorithm;

	
To identify major surgical procedures for lung, the following codes of ICD-9-CM classification will be identified:
 
  
 ICD-9-CM coding related to major surgery on lung	
   
 32.01	ENDOSCOPIC EXCISION OR DESTRUCTION OF LESION OR TISSUE OF BRONCHUS	
 
 32.29	OTHER LOCAL EXCISION OR DESTRUCTION OF LESION OR TISSUE OF LUNG	
 
 32.3	SEGMENTAL RESECTION OF LUNG	
 
 32.4	LOBECTOMY OF LUNG	
 
 32.5	COMPLETE PNEUMONECTOMY	
 
 34.6	SCARIFICATION OF PLEURA	
  
	ICD-9-CM coding related to major surgery on lung		32.01	ENDOSCOPIC EXCISION OR DESTRUCTION OF LESION OR TISSUE OF BRONCHUS	32.29	OTHER LOCAL EXCISION OR DESTRUCTION OF LESION OR TISSUE OF LUNG	32.3	SEGMENTAL RESECTION OF LUNG	32.4	LOBECTOMY OF LUNG	32.5	COMPLETE PNEUMONECTOMY	34.6	SCARIFICATION OF PLEURA
ICD-9-CM coding related to major surgery on lung															
32.01	ENDOSCOPIC EXCISION OR DESTRUCTION OF LESION OR TISSUE OF BRONCHUS														
32.29	OTHER LOCAL EXCISION OR DESTRUCTION OF LESION OR TISSUE OF LUNG														
32.3	SEGMENTAL RESECTION OF LUNG														
32.4	LOBECTOMY OF LUNG														
32.5	COMPLETE PNEUMONECTOMY														

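### KPI 16 counts hospice use over all algorithm patients, living ones included, so differences among sites mix hospice access with mortality and stage mix; a decedent-based version should be added for the site comparison

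*Protocol*

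**What the plan says.** All references are to the protocol.

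- **KPI 16 (section 5.2):** "NUM: Number of patients who underwent hospice care; DEN: Total number of patients identified by the algorithm". It has no restriction by vital status or stage and no time window.
- **KPI 15 (section 5.2), the adjacent row, on integrated home care:** "NUM: Number of patients who underwent IHC service; DEN: Total number of patients identified by the algorithm". This is the same denominator.
- **KPI 12 (section 5.2):** "anti-cancer drug treatment in the last 30 days of life; DEN: Total number of patients identified by the algorithm who deceased". KPI 14 has the same decedent denominator, with the numerator "NUM: Number of patients who performed RT in the last 30 days of life ( excluded palliative treatments".
- **KPI 3 (section 5.2):** "NUM: Number of patients who underwent to lung cancer major surgical resection; DEN: Total number of patients identified by the algorithm". So resected patients belong to the population over which KPI 16 is calculated.
- **Follow-up (section 3):** "The end of data collection will be defined as patient death or 30 June 2018, whichever came first". Patients alive at that date stay in the KPI 16 denominator.
- **General rule (section 7.3):** for each indicator, "the proportion of patients who receive the procedure, in the defined time window, among those eligible will be calculated".
- **Purpose (section 2.1):** the KPIs are to inform on the appropriateness and quality of care among the participating sites.

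**The concern.** Hospice care is given mainly to patients near death. If a hospice percentage is taken over everyone with a new diagnosis, a resected patient who is alive and well adds to the denominator in the same way as a patient who died without hospice. Two sites with identical referral of dying patients will then report different values of KPI 16 if one has more metastatic patients or more deaths before the cut-off.

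At stake is how one of the 16 indicators is read in the primary objective. A site with good survival could look weak on hospice care, and a site with high mortality could look strong, for reasons unrelated to access. Section 5.2 does not split KPI 16 by stage or vital status.

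**Working it through.** The protocol states no expected value for KPI 16, so there is no figure to reproduce. The check is a decomposition.

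**Inputs**
- From the protocol: the KPI 16 numerator and denominator (section 5.2), about 400 patients in all (section 7.2), and three sites (Summary).
- Assumed, because the protocol gives none of them: m, the share of a site's patients dead by cut-off (30% to 70%); a, hospice use among decedents (20% to 60%); s, hospice use among patients alive at cut-off (0% to 10%).

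**Formula**

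KPI 16 = m × a + (1 − m) × s

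**1. Same access, different mortality (a = 40%, s = 0)**

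| m | KPI 16 as written | Hospice use among decedents |
|---|---|---|
| 30% | 0.30 × 0.40 = 12% | 40% |
| 40% | 0.40 × 0.40 = 16% | 40% |
| 50% | 0.50 × 0.40 = 20% | 40% |
| 60% | 0.60 × 0.40 = 24% | 40% |
| 70% | 0.70 × 0.40 = 28% | 40% |

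Between m = 40% and m = 60% the indicator moves by 8 points, a ratio of 1.5, with no difference in access.

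**2. Allowing hospice use among the living (a = 40%)**
- s = 5%: m = 40% gives 0.16 + 0.60 × 0.05 = 19%; m = 60% gives 0.24 + 0.40 × 0.05 = 26%.
- s = 10%: m = 40% gives 0.16 + 0.06 = 22%; m = 60% gives 0.24 + 0.04 = 28%.

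The gap narrows from 8 to 7 to 6 points but does not vanish.

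**3. Same mortality, different access (m = 50%, s = 0)**

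With a = 20%, 40% and 60%, KPI 16 is 10%, 20% and 30%. At equal mortality the indicator is therefore proportional to access.

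**4. The order of sites can reverse (s = 0)**
- Site A, m = 60%, a = 30%: 0.60 × 0.30 = 18.0%.
- Site B, m = 35%, a = 45%: 0.35 × 0.45 = 15.8%.

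Site B has the better access and the lower KPI 16.

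**5. Precision of the two versions (m = 50%, a = 40%, s = 0)**

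Exact Clopper-Pearson limits, with lower = Beta(0.025; x, n − x + 1) and upper = Beta(0.975; x + 1, n − x):

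| | All patients | Decedents |
|---|---|---|
| All sites, 400 patients, 200 deaths | 80/400 = 20.0% (16.2 to 24.3) | 80/200 = 40.0% (33.2 to 47.1) |
| One site, equal split assumed, about 133 patients and 67 deaths | 27/133 = 20.3% (13.8 to 28.1) | 27/67 = 40.3% (28.5 to 53.0) |

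**The case against.** The strongest defence is that KPI 16 is a utilization measure and is consistent as such. Its title, numerator and denominator agree. Section 5.1 lists hospice and home care as utilization, and attaches the end-of-life label to radiotherapy only. KPI 15 is built in the same way, and the rationale names the management of resources as an aim. This stands: the all-patient figure is a valid resource-use figure.

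Three stronger readings are tempting, and the protocol does not support them.

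- *That KPI 16 contradicts KPIs 12 and 14.* Their numerators refer to the last 30 days of life, which exist only for patients who died, so a decedent denominator is forced there. The KPI 16 numerator is not limited to decedents.
- *That KPI 16 reflects mortality instead of access.* Step 3 of the working shows that it responds to access in full proportion when mortality is equal. It mixes the two.
- *That it breaks the rule in section 7.3 on those eligible.* The protocol also uses the word eligible for the whole cohort found by the algorithm, and on that reading KPI 16 complies.

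It can also be said that the study is descriptive, with no target, ranking or between-site test, and that KPI 2 (metastatic share) and the denominators of KPIs 12 and 14 (deaths) let a reader rescale. The first part limits the harm. The second helps only if nobody alive at cut-off used hospice. With a = 40% and s = 10%, dividing all hospice users by deaths gives 22/40 = 55% at m = 40% and 28/60 = 47% at m = 60%, although true use among decedents is 40% at both.

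Two further points leave the argument intact. Section 3 requires at least one anti-cancer drug in 2017, which section 4.1 does not list. If applied, it removes patients treated by surgery alone, but not all resected or living patients. Section 5 limits the data to 2017, while section 3 runs to 30 June 2018. The earlier end would leave more living patients in the denominator.

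**Conclusion.** The point holds in a limited form. KPI 16 as defined is usable as a resource figure, but it is a poor indicator of quality of care among sites because it confounds hospice access with mortality and, through mortality, with stage mix. With a = 40% and s = 0, a mortality contrast of 40% against 60% alone produces 16% against 24%. With s up to 10% the gap is still 6 points.

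These sizes rest entirely on assumed values. The protocol gives no site mortality, hospice use or survival, and three hospitals of one region may differ less than this. The direction of the effect does not depend on those values as long as decedents use hospice more often than patients who are alive. This is a weakly chosen denominator with a cheap improvement. It is not an error that invalidates the primary objective.

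**What to change.** In section 5.2, add a second version of KPI 16:

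- Numerator: deceased patients identified by the algorithm who had at least one hospice care episode.
- Denominator: the one already used in KPIs 12 and 14, "DEN: Total number of patients identified by the algorithm who deceased".

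The numerator must be restricted as well as the denominator; otherwise hospice users alive at cut-off would be counted over deaths. State that this version serves the comparison among sites, and keep the existing all-patient percentage, labelled as resource use alongside KPI 15.

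**Cost.** One extra line in the KPI table. Deaths are already needed for KPIs 6, 12 and 14, so no new data are required.

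**Downsides**
- The denominator is smaller and the interval wider. In the example, the single-site interval widens from 13.8–28.1% to 28.5–53.0%.
- Follow-up to 30 June 2018 is about 6 to 18 months from a 2017 index admission, so decedents are the earlier deaths. Hospice users alive at cut-off appear only in the all-patient figure, which is a reason to report both.
- The decedent version removes the arithmetic dependence on the share who died. It does not adjust for other differences in case mix among decedents.
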